**8.3.1 Ethics Committee/Institutional Review Board Notification by Investigator**

Reports of AEs (including follow-up information) must be submitted to the EC or IRB according to their specific reporting requirements. Copies of each report and documentation of EC/IRB notification and receipt must be kept with the investigator's study files.

## **8.4 Recording of Adverse Events**

All protocol defined AEs occurring during the study period must be recorded; this includes events that occur between visit intervals. The clinical course of each event should be followed until resolution or stabilization or until it is determined at the end of the study that the AE will not resolve.

## **8.5 Medical Monitoring**

It is the responsibility of the investigator to oversee the safety of the study at his/her center. This safety monitoring will include careful assessment and appropriate reporting of AEs, as previously noted. Stryker will conduct formal investigations via the Product Surveillance Department of those AEs which are submitted through our PER System.

# **9 Statistical Plan**

## **9.1 Efficacy**

### **9.1.1 Primary Efficacy Parameters**

The primary efficacy parameter is the success rate at 2 years postoperative with the Triathlon Tritanium Tibial Baseplate for Cohort 1 (cementless), where success is defined as absence of tibial baseplate revision and/or removal for aseptic loosening at 2 years postoperative.

### **9.1.2 Secondary Efficacy Parameters**

The secondary efficacy parameters include:

- The all-cause survivor function of the Triathlon Tritanium Tibial Baseplate by Kaplan-Meier method for Cohort 1 (cementless).
- The all-cause survivor function of the Triathlon Tritanium Patella by Kaplan-Meier method for Cohort 1 (cementless).
- The all-cause revision and/or removal rate of the Triathlon Tritanium Tibial Baseplate for Cohort 1 (cementless).

CONFIDENTIAL

This material is the property of Stryker Orthopaedics. Do not disclose or use except as authorized in writing by Stryker.

- The all-cause revision and/or removal rate of the Triathlon Tritanium Patella for Cohort 1 (cementless).
- 2011 KSS, SF-12 and OKS scores at 2 year for both cohorts.

### **9.1.3 Primary Efficacy Analysis**

The primary hypothesis to be tested will be that the success rate at 2 years postoperative with the Triathlon Tritanium Tibial Baseplate for Cohort 1 (cementless) is not worse than 99% with a non-inferiority margin of 2%.

That is, the following hypothesis will be tested:

$H_0: Pt \leq 99\% - 2\%$   $H_A: Pt > 99\% - 2\%$

Here, Pt is the success rate at 2 years postoperative with the Triathlon Tritanium Tibial Baseplate for Cohort 1 (cementless).

A 90% two-sided confidence interval will be computed for the success rate at 2 years. If the lower bound of the confidence interval is greater than 97%, then the non-inferiority hypothesis will be supported.

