## **9.3 Missing Data**

Missing data in OKS will be imputed when calculating the OKS score using the method recommended by the new OKS scoring system. Missing data in 2011 KSS will be imputed when calculating KSS scores with the method recommended in the user manual of the 2011 Knee Society knee scoring system. No other missing data will be imputed.

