## **9.4 Statistical Methodology**

### **9.4.1 Data Summary**

Descriptive statistics will be computed for all baseline conditions and demographic parameters. That is, for continuous data, the N, mean, median, standard deviation, minimum and maximum will be computed. For categorical data, the frequency will be computed. The data will be presented by appropriate subgroups (e.g., center).

A Kaplan-Meier survivorship curve will be displayed for revision and/or removal of the Triathlon Tritanium Tibial Baseplate for aseptic loosening for cementless cohort.

For the additional data collected according to Section 2.1.3, data will be summarized according to visits and cohorts. For parameters represented by continuous variables (e.g., ROM), the summaries will consist of the N, mean, median, standard deviation, minimum, and maximum values. For categorical variables (e.g., Gender from

CONFIDENTIAL

This material is the property of Stryker Orthopaedics. Do not disclose or use except as authorized in writing by Stryker.

Demographics), the frequency and percentage in each category will be presented. A paired t-test will be performed to evaluate the change in clinical and patient outcomes, preoperative to 10 years for cases with the Triathlon Tritanium Tibial Baseplate in cementless cohort. The 2011 KSS, OKS, and SF-12 will be compared and be presented with respect to improvement from preoperative to postoperative scores for both cohorts when applicable.

For the Follow-up Questionnaire, frequency and percentage will be computed for each category according to visits and cohorts. Applicable lists based on the Follow-up Questionnaire will be generated to capture AEs.

For radiographic data, data will be presented according to visits and cohorts for available parameters. Frequency and percentage will be computed for radiolucency according to visits. Radiographs will be evaluated according to the guidelines of The Knee Society total knee arthroplasty roentgenographic evaluation and scoring system.

Documentation of statistical analyses will utilize SAS software version 9.1.3 or higher.

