#### **9.4.2 Sample Size Justification**

With a reference value of 99% for the success rate at 2 years, under the assumptions of 5% significance level (or 95% one-sided confidence interval), 95% power, 2% non-inferiority margin, the sample size is 267. After factoring a 15% lost to follow-up rate, the final sample size is 315 for the primary endpoint. An enrollment objective of 356 cases in Cohort 1 (cementless) was selected to power the primary objective of this study. In addition, 144 cases will be enrolled in Cohort 2 (cemented) to serve as a concurrent control for one of the secondary objectives.

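### Section 9.1.3 names no estimator or interval for the 2-year success rate; the natural reading, a proportion of knees with known status, drops unfailed follow-up that the planned Kaplan-Meier curve would use.

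*Combined protocol and SAP*

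**What the plan says.** Section 9.1.3 rests the primary test on one sentence about estimation, "A 90% two-sided confidence interval will be computed for the success rate at 2 years", and one about the decision: "If the lower bound of the confidence interval is greater than 97%, then the non-inferiority hypothesis will be supported". No estimator, interval method or rule for knees without 2-year status is given.

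Other sections bear on what is meant:

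- Section 9.4.4 bases the primary analysis on a per protocol set limited to non-censored subjects who can be evaluated for efficacy.
- Section 9.3 provides item-level imputation for the OKS and 2011 KSS, then states "No other missing data will be imputed".
- Section 9.4.2 sizes the test as a single proportion and treats losses as removed: "After factoring a 15% lost to follow-up rate, the final sample size is 315 for the primary endpoint".
- Section 10.3 counts baseplate revision or removal for aseptic loosening as a failure of the primary endpoint. It ends the subject's participation on baseplate revision for any reason.
- Section 9.4.1 plans a survival curve for this same event, but only as a display: "A Kaplan-Meier survivorship curve will be displayed for revision and/or removal of the Triathlon Tritanium Tibial Baseplate for aseptic loosening for cementless cohort".

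**The concern.** Taken together, these sections point to a proportion whose denominator is the knees with known status at 2 years. That treats the two outcomes unequally. A knee revised for loosening at 8 months is a known failure from that day and stays in. A sound knee lost at 20 months is removed, along with its 20 months of unfailed follow-up. Successes are thinned by the full loss rate and failures by less, so the failure rate tends to come out too high.

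Two things are at stake. The test gives up some chance of passing with data already in hand. The trial could also report two different 2-year aseptic-loosening figures from the same knees: the tested rate and the 24-month point on its own curve. Leaving estimator and interval open also allows the choice to be made after the data are seen.

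**Working it through.** **Inputs from the plan.** Reference success 99%, margin 2 points, one-sided 5%, power 95%, n = 267, 15% loss giving 315, and 356 enrolled in Cohort 1 (section 9.4.2); pass if the lower 90% limit exceeds 97% (section 9.1.3).

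**Assumed, because the plan is silent.** True failure of 1% (the reference rate), the timing of failures and losses within 24 months, the interval method, and loss unrelated to failure unless stated.

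**The plan's own figure.** n = 0.99 × 0.01 × (1.645 + 1.645)² / 0.02² = 267.8, against 267 stated. 267 / 0.85 = 314.1, against 315 stated. So the sizing is a one-sample proportion by normal approximation, with lost knees contributing nothing. With 15% loss, 356 × 0.85 = 302.6 knees keep known status. The pass probabilities below fall short of 95% partly because the actual rule works on whole failures: at n = 267 the exact pass probability is 86.8% with a Wald interval and 72.1% with Wilson or Clopper-Pearson (exact).

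**Size of the bias.** Let L be the loss fraction. With failure and loss times uniform over 24 months, a failure is seen with probability 1 − L/2, and an unfailed knee is retained with probability 1 − L.

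- Uniform timing, L = 0.15: seen failures 0.01 × 0.925 = 0.00925; retained successes 0.99 × 0.85 = 0.8415; 0.00925 / 0.85075 = 1.09%.
- All losses just before 24 months: 0.01 / (0.01 + 0.8415) = 1.17%.
- All losses at the start: 1.00%, no bias.

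Kaplan-Meier averages 1.00% in each case.

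**Pass probability.** Simulation with 36,000 trials per scenario, 356 knees, true failure 1%, 15% loss. Each cell gives the known-status proportion, then Kaplan-Meier with the matching interval (plain Greenwood, Wilson on effective n, exact on effective n).

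| Timing | Proportion's mean failure | Wald type | Wilson type | Exact type |
|---|---|---|---|---|
| All losses at start | 1.00% | 91.2 → 91.2% | 79.8 → 79.8% | 72.8 → 72.8% |
| Both uniform | 1.09% | 88.3 → 90.5% | 75.1 → 78.1% | 67.9 → 76.7% |
| Late losses, uniform failures | 1.13% | 86.5 → 93.5% | 72.8 → 83.2% | 65.6 → 77.7% |
| Late losses, early failures | 1.15% | 85.5 → 93.5% | 71.1 → 84.6% | 64.0 → 80.4% |
| All losses just before 2 years | 1.17% | 84.8 → 93.1% | 70.0 → 85.1% | 63.1 → 85.0% |

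The like-for-like gain is therefore 2 to 9 points under uniform timing and 0 to about 22 overall. Kaplan-Meier with log-log limits passes 76.9% of the time under uniform timing.

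**Type I error at a true 97% success rate** (356 knees, 15% loss, uniform timing). Known-status proportion: Wald 6.8%, Wilson 2.8%, exact 2.0%. Kaplan-Meier: plain Greenwood 9.0%, log-log 3.0%. Under the two later-loss timings that were run, log-log gives 4.0% and 4.4%, still below 5%.

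**If loss depends on failure.** With 15% loss overall and a fraction q of failing knees lost before their failure is seen, the proportion estimates 0.01 × (1 − q) / 0.85. At q = 0.15 this is 1.00%; at q = 0.25, 0.88%; at q = 0.50, 0.59%. The direction reverses once q exceeds 15%.

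**The case against.** The strongest reply is that the plan nowhere states a simple proportion. That is correct: the estimator is an inference from sections 9.3, 9.4.2 and 9.4.4. Section 9.4.1 shows that a curve for this event was at least in mind. But if Kaplan-Meier is intended for the test, section 9.1.3 has to say so.

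Second, at the stated loss rate and uniform timing the bias is 0.09 points against a 2-point margin, and it works against the sponsor. It does not manufacture non-inferiority. This stands.

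Third, part of the gain comes from the interval. About 303 knees remain after 15% loss, which sits on a step of the exact rule: 3 failures are allowed at n = 302 and 4 at n = 303. Naming a Wilson interval for the ordinary proportion would already give 75.1%. Against that, log-log Kaplan-Meier gains about 2 points under uniform timing and loses about 5 (74.9% against 79.8%) if every loss falls at the start. This stands too, so the case for Kaplan-Meier rests on using all the follow-up and agreeing with the displayed curve as well as on power.

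Fourth, real loss may be smaller than modelled. Section 7.5.1 allows a questionnaire by mail, online or telephone when a visit cannot be held, and section 10.3 requires three calls and a certified letter before a subject counts as lost. A missed visit need not mean unknown implant status.

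A reader might also infer a cost of 8 to 15 points. An exact bound with uniform timing does give about 68% against 76% at 15% loss and about 60% against 75% at 25% loss. The documents do not support this as a general figure: they fix neither the exact interval nor the timing, and they never state 25% loss, which is only what 267 / 0.75 = 356 would imply.

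**Conclusion.** The concern holds in a limited form. Section 9.1.3 leaves the estimator and interval of the primary test open, and the most natural reading discards unfailed follow-up that a curve already planned would use. At 356 knees, 1% true failure and the stated 15% loss, the failure estimate is too high by 0 to 0.17 percentage points. The cost in pass probability is 2 to 9 points under uniform timing and 0 to about 22 across the timings examined. It would be larger at 25% loss, which the plan does not state.

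These figures assume that loss is unrelated to failure. It would be wrong to conclude that the rate must overstate failure: if more than 15% of failing knees are lost before their failure is seen, it understates it, and Kaplan-Meier does not cure that. The point is a cheap improvement to an unspecified analysis, not a threat to the trial's validity.

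**What to change.** In section 9.1.3, define the 2-year success rate as the Kaplan-Meier estimate at 24 months of freedom from baseplate revision or removal for aseptic loosening. Use all implanted Cohort 1 knees, censored at the last date implant status is known, and align the primary population in section 9.4.4 with this.

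- State that deaths and baseplate revisions for other reasons are censored at that date, and add a cumulative-incidence sensitivity analysis that treats them as competing events.
- Use a two-sided 90% log-log interval, with an exact bound if there are no failures. Do not use plain Greenwood limits, which give about 9% type I error.
- Keep the 97% rule.
- Report the known-status proportion, with its interval method named, as a sensitivity analysis.

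The cost is a few sentences of SAP text; no new data are needed and the curve is already planned. The downside is that Kaplan-Meier assumes non-informative censoring, which should be stated.

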### **9.1.4 Secondary Efficacy Analysis**

For Cohort 1 (cementless), the all-cause survivor function of the Triathlon Tritanium Tibial Baseplate will be produced by Kaplan-Meier method; The all-cause survivor function of the Triathlon Tritanium Patella will be produced by Kaplan-Meier method; The all-cause revision and/or removal rate of the Triathlon Tritanium Tibial Baseplate will be calculated; The all-cause revision and/or removal rate of the Triathlon Tritanium Patella will be calculated. The 2011 KSS, SF-12 and OKS scores will be compared between Cohort 1 (cementless) and Cohort 2 (cemented) at 2 years postoperative using applicable statistical methods.

CONFIDENTIAL

This material is the property of Stryker Orthopaedics. Do not disclose or use except as authorized in writing by Stryker.

## **9.2 Safety**

### **9.2.1 Safety Parameters**

Safety parameters include all protocol-defined AEs as well as revision and/or removal rates. For details regarding protocol-defined AEs, see Section 8.1.

### **9.2.2 Safety Analyses**

The frequency and percentage of all protocol-defined AEs will be tabulated. For details regarding protocol-defined AEs, see Section 8.1.

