## Study Synopsis

Title	A prospective, post-market, multi-center study of the outcomes of the Triathlon Tritanium Knee System
Short Title	Triathlon Tritanium Knee Outcomes Study
Protocol Number	74
Phase	Post-market
Methodology	
This study is a prospective, non-randomized evaluation of the Triathlon Tritanium Knee System for primary total knee arthroplasty (TKA) with a cementless application in a consecutive series of patients who meet the eligibility criteria.
 
Cohort 1 (cementless): The first 356 cases enrolled will receive the Triathlon Tritanium Tibial Baseplate, Triathlon Tritanium Patella, Triathlon CR or PS Beaded Femur with PA and the Triathlon Tibial Insert. All components in this cohort must be used in a cementless application.
 
Cohort 2 (cemented): An additional 144 cases will receive the Triathlon Cemented Tibial Baseplate, Triathlon Cemented Patella, Triathlon CR or PS Cemented Femur and Triathlon Tibial Insert. All components in this cohort must be used in a cemented application.
 
The study uses literature control for the primary endpoint and a concurrent control (Cohort 2) for secondary endpoints.

Study Duration	
Approximate 12-year total duration
 

• Enrollment period of 24 months

• Follow-up of each primary Cohort 1 (cementless)TKA case to 10 years

• Follow-up of each primary Cohort 2 (cemented) TKA case to 5 years.

Study Center(s)	5-10 centers. The same center may be included in both arms. Conversely, a center may choose to participate in only a single arm.

CONFIDENTIAL

This material is the property of Stryker Orthopaedics. Do not disclose or use except as authorized in writing by Stryker.

Hypothesis	The success rate of the Triathlon Tritanium Knee, defined as absence of revision for aseptic loosening of the tibial baseplate at 2 years, is no worse than rates reported in the literature for cemented devices.

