## **2.2 Safety**

All operative site events occurring at any time, as well as all serious adverse events (SAEs) occurring in the perioperative period (intraoperative to hospital discharge), are collected and compared to published data. It is expected that the AE rates reported for the Triathlon Tritanium Tibial Baseplate and Patella will be comparable to those reported in the literature for cemented primary total knee systems on the market. Details regarding AE definitions, recording and reporting are in Section 8 of this protocol, Adverse Events.

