### **3.4 Estimated Study Duration**

The enrollment period is estimated to be 24 months; cases for Cohort 1 (cementless) are evaluated as per the evaluation schedule until each case reaches 10 years. Cases for Cohort 2 (cemented) are evaluated as per the evaluation schedule until each case reaches 5 years. The total estimated study duration from enrollment to close-out activities is 12 years.

To allow for a learning curve with the use of the device, enrollment of cases into the study commences when three cases have been completed at the center using the Triathlon Tritanium Tibial Baseplate and Triathlon Tritanium Patella.

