## **8 Adverse Events**

### **8.1 Reporting of Adverse Events**

The AE reporting requirements for this study are as follows:

- All AEs that are operative site related, regardless of seriousness or time of occurrence.
- All AEs that meet the definition of serious and occur within the perioperative period (intraoperative to hospital discharge)

CONFIDENTIAL

[figure not shown]
This material is the property of Stryker Orthopaedics. Do not disclose or use except as authorized in writing by Stryker.

On postoperative functional evaluations, investigators and SCs are prompted to question subjects as to whether they have seen a doctor for any reason, been hospitalized for any reason or have a current impediment to their function.

Additionally, SCs are responsible for following up with the subjects regarding any questionable responses received on the Follow-up Questionnaire. If it is determined upon this further investigation that a protocol-defined AE has occurred, the SC will be responsible for completing an AE eCRF, submitting the event to Stryker and reporting to the IRB/EC, as required.

The following decision tree facilitates identification of AEs for which reporting is required under this study protocol:

Figure 2: Adverse Event Decision Tree

CONFIDENTIAL

This material is the property of Stryker Orthopaedics. Do not disclose or use except as authorized in writing by Stryker.

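### Section 9.2.2 gives operative-site adverse events only as a crude percentage with no time basis and an undefined denominator, so it cannot support the comparison with published rates intended in Section 2.2

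*Combined protocol and SAP*

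**What the plan says.** Section 2.2 covers two kinds of event: operative-site events at any time, and serious events from surgery to hospital discharge. Both are to be set against published data, and the sponsor expects AE rates for the Tritanium baseplate and patella that "will be comparable to those reported in the literature for cemented primary total knee systems on the market". Section 12.5 repeats the aim of comparing the device with published results.

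The analysis is one sentence in Section 9.2.2: "The frequency and percentage of all protocol-defined AEs will be tabulated". Section 12.3 adds only that AE rates and revision/removal rates will be tabulated. Section 9.4.1 provides lists from the Follow-up Questionnaire to capture AEs, but no time-specific AE analysis.

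The events accrue over time. Section 8.1 makes reportable "All AEs that are operative site related, regardless of seriousness or time of occurrence", and its reporting period runs from consent to study completion. Section 3.4 says "cases for Cohort 1 (cementless) are evaluated as per the evaluation schedule until each case reaches 10 years" and "Cases for Cohort 2 (cemented) are evaluated as per the evaluation schedule until each case reaches 5 years". Time at risk also varies within a cohort: Section 9.4.2 allows for 15% loss to follow-up for the 2-year endpoint, and Section 10.3 ends participation when a Tritanium baseplate is revised or removed for any reason.

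Section 9.4.4 limits the safety population to non-censored subjects who received the devices and does not say what non-censored means.

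**The concern.** A crude percentage estimates a risk only if everyone counted was observed for the same stated period. Here the numerator can grow for as long as follow-up lasts, and the denominator may or may not include cases that left early. Published AE rates refer to some length of follow-up, so a figure with none attached has nothing to be matched to.

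What is at stake is the statement that the device's AE rates are comparable with those of cemented systems. Depending on when the table is cut and who is counted, the same underlying risk could look better or worse than the literature. The primary endpoint is not touched.

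**Working it through.** **The plan's own figures.** No AE rate or AE sample size is stated. The one related input is the 15% loss in Section 9.4.2, where the arithmetic reproduces: 0.99 × 0.01 × (1.645 + 1.645)² / 0.02² = 267.8, against 267 stated; and 267 / 0.85 = 314.1, rounded up to 315 as stated. The AE point does not depend on these sample sizes. The 15% is used only to choose a plausible loss rate.

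**Assumptions.**
- First operative-site event at a constant hazard *h* of 0.5 to 5% per year, the same throughout. The documents give no value.
- Annual loss of 5 to 8%, i.e. *m* = −ln 0.95 = 0.0513 to −ln 0.92 = 0.0834. This includes 15% over 2 years, since 1 − √0.85 = 7.8% per year. Continuing that loss beyond year 2 is an extrapolation.

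**Step 1: effect of follow-up length alone.** With no loss, the percentage with an event by time *T* is 1 − exp(−*hT*).

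| *h* per year | 5 years | 10 years | Ratio |
|---|---|---|---|
| 0.5% | 2.5% | 4.9% | 1.98 |
| 1% | 4.9% | 9.5% | 1.95 |
| 2% | 9.5% | 18.1% | 1.90 |
| 5% | 22.1% | 39.3% | 1.78 |

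With loss, and lost cases kept in the denominator, the crude percentage is *h*/(*h*+*m*) × [1 − exp(−(*h*+*m*)*T*)]. Over the same hazards and 5 to 8% annual loss, the ratio of 10-year to 5-year figures is 1.51 to 1.75. The overall range is therefore about 1.5 to 2.0.

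**Step 2: if many events are early.** Let a share *e* of cases have an early event and the rest follow a constant hazard: *e* + (1 − *e*)[1 − exp(−*hT*)]. With *e* = 10% and *h* = 0.5% per year, this gives 12.2% at 5 years and 14.4% at 10 (ratio 1.18). With *e* = 5% and *h* = 2% per year, it gives 14.0% and 22.2% (ratio 1.58). The range is about 1.2 to 1.6.

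**Step 3: effect of the denominator, at *h* = 2% per year.** The proportion still followed and event-free is exp(−(*h*+*m*)*T*). If lost cases are excluded, the percentage is events / (events + still followed).

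| Time | True risk | Lost cases kept | Lost cases excluded |
|---|---|---|---|
| 2 years | 3.9% | 3.6 to 3.7% | 3.73/(3.73+86.71) = 4.1% to 3.61/(3.61+81.32) = 4.3% |
| 5 years | 9.5% | 7.8 to 8.4% | 8.41/(8.41+70.01) = 10.7% to 7.81/(7.81+59.64) = 11.6% |
| 10 years | 18.1% | 12.5 to 14.3% | 14.30/(14.30+49.02) = 22.6% to 12.47/(12.47+35.56) = 26.0% |

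Keeping lost cases biases the figure down and excluding them biases it up. Section 9.4.4 does not say which applies. The bias is small at 2 years and grows with follow-up.

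**The case against.** The strongest reply is that the AE analysis is descriptive. Section 2.2 states an expectation, with no hypothesis, test or decision rule. Section 9.2.2 leaves the time window open but does not instruct anyone to pool unequal follow-up, and Section 16 anticipates publications at 2, 5 and 10 years, so tables at common times may well be produced. Some of the safety data are also not at risk: perioperative serious events share one short window in both cohorts, and revision/removal in Cohort 1 already has Kaplan-Meier curves (Sections 9.1.4 and 9.4.1). The hazards used above are assumed, and how far a crude figure misses a given publication depends on how that publication reports AEs.

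Most of this stands, and it limits the point to operative-site AEs. It does not remove it. Publication dates are not analysis cut-offs, and even a table cut at 5 or 10 years would still face dropout and an undefined denominator.

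A reader might go further and infer that the longer-followed cementless cohort will be made to look worse than the cemented one; at 2% per year with 5 to 8% loss the crude figures would differ 1.6 to 1.7-fold. The documents do not support this as a planned result. Section 2.2 compares Tritanium with the literature, Section 9.2.2 does not mention cohorts, and Section 9.4.2 makes Cohort 2 a control for one secondary objective, which Section 9.1.4 shows to be the 2-year scores. The difference between 10 and 5 years matters only if the cohorts are tabulated side by side. Nor can one say that dropout makes the crude figure too low, because the direction depends on how non-censored is read.

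**Conclusion.** The point holds for operative-site AEs. The stated method gives a percentage that depends on length of follow-up and on the handling of lost cases, and it cannot support the literature comparison in Section 2.2. This follows from Sections 2.2, 8.1, 9.2.2 and 9.4.4 without any assumed rate.

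Its size does rest on assumptions: a constant hazard of 0.5 to 5% per year (or a mix of early and later events) and loss continuing at 5 to 8% per year. The distortion from follow-up length is then about 1.2 to 2.0-fold between 5 and 10 years. At 2% per year the denominator alone moves a true 5-year risk of 9.5% to anywhere from 7.8 to 11.6%. The plan should be changed, but neither the primary endpoint nor the perioperative safety data are in question.

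**What to change.** In Section 9.2.2, keep the frequency and percentage for perioperative serious events. For operative-site AEs, report by cohort either Kaplan-Meier or cumulative-incidence estimates with 95% intervals at 2 and 5 years (and 10 years for Cohort 1 only), or events per 100 knee-years. Put all implanted cases in the risk set and censor lost or terminated cases at exit; this replaces the non-censored restriction in Section 9.4.4 for this analysis. State that comparison with the literature, and any side-by-side display of the cohorts, is made only at matching times.

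One detail needs care. Section 10.3 dates a loss to follow-up by the sponsor's approval of termination, which comes after the contact attempts have failed, so the censoring date should be the last contact with AE information.

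The cost is SAP wording and table programming. Event onset, visit and termination dates are already on the Appendix F forms, so no new data are needed.
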